There are two stages to this study: a dose-escalation stage and a cohort-expansion stage. During the dose-escalation stage, 10 dose-escalation cohorts of 3–6 patients each will be enrolled in order to identify a safe and tolerable dose of each agent to be administered during the cohort-expansion stage, i.e., the potential recommended Phase II/III dose combination. Approximately 20 additional patients will be enrolled into each of (minimally) two expansion cohorts during the cohort-expansion stage. One cohort will consist of patients who have progressed on vemurafenib monotherapy immediately prior to enrolling in this trial, and the other will consist of previously untreated or treated patients without prior exposure to any BRAF or MEK inhibitor therapy. Therefore, approximately 130 patients (not including patients treated with cobimetinib monotherapy) will be enrolled in the trial at approximately 7-10 sites in total in the United States and Australia.

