Figure 4: Dose-Escalation Plan for the Combination of Vemurafenib and Cobimetinib Administered on a 14/14 Schedule

* Simultaneous enrollment in Cohorts 1A (Figure 5), 2, and 3

Figure 5: Dose Escalation Scheme for the Combination of Vemurafenib and Cobimetinib Administered Either on a 21/7 Day or a Continuous Schedule

* Declaration of Cohort 1A safety and tolerability will trigger enrollment in several cohorts: Cohort 1B (under Amendment D), Cohort 1C (pending approval of Amendment E), and Cohort 1A expansion cohorts of patients who progressed on vemurafenib immediately prior to enrolling this trial (n = 20) and previously untreated with vemurafenib or other BRAF or MEK inhibitor (n = 20); see Section 3.1.

If the Cohort 1 dose combination is safe and tolerable as per the rules for dose-limiting toxicity (Section 3.1.4), escalation will continue with simultaneous enrollment of Cohort 1A (Figure 5) when available, Cohort 2, and Cohort 3 (Figure 4). Cohort 2 will evaluate the combination of vemurafenib at a dose of 720 mg bid and cobimetinib at 80 mg/day on a 14/14 day schedule, and Cohort 3 will evaluate the combination of vemurafenib at a dose of 960 mg bid and cobimetinib at 60 mg/day on a 14/14 day schedule. Cohort 2A (Figure 4) may be enrolled only if the dose combination tested in Cohort 2 is declared safe and tolerable. Enrollment in Cohort 4 may occur only if the dose combinations tested in both Cohorts 2 and 3 are declared safe and tolerable. Cohort 4 will evaluate the combination of vemurafenib at 960 mg bid and cobimetinib at 80 mg/day on a 14/14 day schedule. If the Cohort 4 combination is safe and tolerable, further escalation will occur with enrollment in Cohort 5. Cohort 5 will evaluate the combination of both

vemurafenib and cobimetinib at their monotherapy MTDs (960 mg bid and 100 mg/day, respectively, 14/14 day schedule,).

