Patients without prior treatment for locally advanced/unresectable or metastatic melanoma or those previously treated but without prior exposure to any BRAF or MEK inhibitor therapy:

Inclusion of this category of patient will allow a more expedient assessment of the optimal dose(s) and schedule(s) for the vemurafenib/ cobimetinib combination as well as a preliminary assessment of the activity of this combination in relationship to that observed historically with vemurafenib monotherapy.

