4.2 Inclusion Criteria

A patient may be included if the answer to all of the following statements is “yes.”

Disease-Specific Inclusion Criteria:

1. Patients with histologically confirmed melanoma, either unresectable Stage IIIc or Stage IV metastatic melanoma, as defined by AJCC
2. Measurable disease per Response Evaluation Criteria in Solid Tumors (RECIST) v1.1 (see [Appendix 1](#))
3. ECOG performance status of ≤ 1 (see [Appendix 2](#))

General Inclusion Criteria:

4. Male or female patient age ≥ 18 years
5. Able to participate and willing to give written informed consent prior to performance of any study-related procedures and to comply with the study protocol
6. Patients must
 - a.) be previously untreated for locally advanced/unresectable or metastatic melanoma OR
 - b.) previously treated but without prior exposure to any BRAF or MEK inhibitor therapy OR

c.) progressed on vemurafenib while participating in a Phase I (including clinical pharmacology studies), II, or III clinical study or EAP immediately prior to enrollment in this study OR

d.) progressed on vemurafenib administered in a postmarketing setting immediately prior to enrollment in this study.

Note: Participants in an antecedent vemurafenib clinical trial or those who progress while receiving the drug in a postmarketing setting should exhibit evidence of discordant/mixed progression and not have received intervening antimelanoma therapy except with vemurafenib. The presence of V600E mutation in melanoma tumor tissue must be documented using the **cobas** BRAF^{V600} mutation test in all patients.

7. Life expectancy \geq 12 weeks
8. Patients must have fully recovered from the effects of any major surgery or significant traumatic injury within 14 days from the first dose of study treatment.
9. Adequate hematologic and end organ function, defined by the following laboratory results obtained within 2 weeks prior to first dose of study drug treatment:
 - ANC \geq $1.5 \times 10^9/L$
 - Platelet count \geq $100 \times 10^9/L$
 - Hemoglobin \geq 9 g/dL
 - Albumin \geq 2.5 g/dL
 - Bilirubin \leq 1.5 X ULN
 - AST, ALT, and ALP \leq 2.5 X ULN, with the following exceptions:
 - Patients with documented liver metastases: AST and /or ALT \leq 5 X ULN
 - Patients with documented liver or bone metastases: ALP \leq 5 X ULN

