4.3 Exclusion Criteria

A patient will be excluded if the answer to any of the following statements is "yes."

Cancer-Related Exclusion Criteria:

1. History of prior significant toxicity from another RAF or MEK pathway inhibitor requiring discontinuation of treatment
2. Allergy or hypersensitivity to components of the cobimetinib or vemurafenib formulations
3. Palliative radiotherapy within 2 weeks prior to first dose of study drug treatment in Cycle 1, Day 1
4. Experimental therapy within 4 weeks prior to first dose of study drug treatment in Cycle 1, Day 1 except vemurafenib
5. Major surgical procedure or significant traumatic injury within 14 days prior to first dose of study drug treatment in Cycle 1, Day 1 or anticipation of the need for major surgery during the course of study treatment
6.
 - a) For patients who participated in an antecedent vemurafenib study or progressed while receiving vemurafenib in a postmarketing setting: administration of any systemic anti-melanoma therapy other than vemurafenib during the interval between documentation of progression coincident with their vemurafenib exposure and consideration for this study will render the patient ineligible.
 - b) For previously untreated patients: no prior systemic, anti-cancer therapy (e.g., biologic or other targeted therapy, chemotherapy or hormonal therapy) for unresectable, locally advanced or metastatic melanoma disease. Note: Prior treatment in the adjuvant setting for previously resected melanoma is allowed.
 - c) For previously treated patients: no prior exposure to any BRAF or MEK inhibitor therapy; prior treatment with systemic chemotherapy or ipilimumab is allowed.
7. Active malignancy other than melanoma that could potentially interfere with interpretation of the PD or efficacy measures

Exclusion Criteria Based on Organ Function

Ocular:

8. Evidence of visible retinal pathology, as assessed by ophthalmologic examination, that is considered a risk factor for retinal vein thrombosis
9. Intraocular pressure > 21 mm Hg as measured by tonometry
10. History of RVO
11. Predisposing factors to RVO, including uncontrolled hypertension (Grade ≥ 2 at screening), uncontrolled diabetes (e.g., untreated or inadequately treated Grade ≥ 2 glucose intolerance), uncontrolled hyperlipidemia (e.g., untreated or inadequately treated Grade ≥ 2 hypercholesterolemia or hypertriglyceridemia) or hypercoagulable state

Cardiac:

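### The adjuvant note in exclusion 6b sets no drug-class limit, so a patient given an adjuvant BRAF or MEK inhibitor can enter an expansion group that Section 3.1 and the Figure 5 note describe as unexposed

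*Combined protocol and SAP*

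**What the plan says.** Section 4.2, item 6, gives separate routes into the trial. Route 6a is to "be previously untreated for locally advanced/unresectable or metastatic melanoma OR" one of the alternatives that follow. It carries no condition on BRAF or MEK inhibitors. Route 6b, for the previously treated, does.

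Section 4.3, exclusion 6, mirrors this. Item 6b bars earlier systemic therapy, targeted therapy included, but only when given for advanced disease. It ends: "Note: Prior treatment in the adjuvant setting for previously resected melanoma is allowed." Item 6c reads: "For previously treated patients: no prior exposure to any BRAF or MEK inhibitor therapy; prior treatment with systemic chemotherapy or ipilimumab is allowed."

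Two other exclusions bear on such a patient. Exclusion 1 covers "History of prior significant toxicity from another RAF or MEK pathway inhibitor requiring discontinuation of treatment". Exclusion 4 covers experimental therapy in the four weeks before dosing, and exempts vemurafenib.

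Section 3.1, like the synopsis, describes the two expansion cohorts. One is for vemurafenib progressors, and "the other will consist of previously untreated or treated patients without prior exposure to any BRAF or MEK inhibitor therapy". The Figure 5 note in Section 3.1.1 describes the second Cohort 1A expansion group as "previously untreated with vemurafenib or other BRAF or MEK inhibitor (n = 20").

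Section 3.3 says that including non-progressors allows a "preliminary assessment of the activity of this combination in relationship to that observed historically with vemurafenib monotherapy".

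**The concern.** The eligibility criteria decide who enters, and they admit a patient whom the cohort description rules out. A patient given a BRAF or MEK inhibitor after resection, who later relapses with unresectable disease and has had nothing since, passes 6a and 6b. Only a toxicity-related stop (exclusion 1) or recent experimental use (exclusion 4) would prevent entry.

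The stake is how the non-progressor expansion results are read. That group is the trial's view of the combination in patients new to the pathway inhibitors, and its activity is to be related to past vemurafenib monotherapy results. A patient with earlier exposure may respond differently but would be counted as naive in objective response rate (ORR), duration of response (DOR) and progression-free survival (PFS). With about 20 patients per cohort, a few can move a descriptive rate.

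**Working it through.** **Step 1: which category does an adjuvant-only patient fall into?** The abbreviations under Tables 5 and 8 define previously treated patients (PTPs) as those treated for locally advanced, unresectable or metastatic melanoma. Someone treated only in the adjuvant setting is not a PTP. Table 8 defines previously untreated patients (PUPs) by the absence of treatment for advanced disease, with no inhibitor condition. The patient is therefore a PUP.

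**Step 2: does a criterion stop a PUP with adjuvant BRAF or MEK inhibitor exposure?**

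| Criterion | Applies? |
|---|---|
| Inclusion 6a | Met; no inhibitor condition |
| Inclusion 6b, exclusion 6c | No; written for the previously treated |
| Exclusion 6b | No; limited to therapy for advanced disease, adjuvant therapy allowed |
| Exclusion 1 | Only after discontinuation for significant toxicity |
| Exclusion 4 | Only experimental therapy within 4 weeks, not vemurafenib |

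**Step 3: how do the other sections describe the group?**

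| Place | Are PUPs required to be unexposed? |
|---|---|
| Synopsis and 3.1, expansion description | Yes, on the natural reading |
| Figure 5 note | Yes |
| 3.2 and Table 8 | Not stated; the condition follows the previously treated |
| Synopsis, 2.1, 3.1 and 3.1.1, population sentence | Unclear; it covers those previously treated, which in ordinary words could include adjuvant treatment but under the PTP definition does not |

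**Step 4: the plan's own figure.** Section 8.3 gives more than 98.8% for at least one response among 20 patients at a true rate of 20%. The formula is 1 − (1 − p)^n:

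1 − 0.8^20 = 0.9885, which reproduces it.

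The wording change leaves n = 20, so the figure stands. If k of the 20 were exposed and never responded, 1 − 0.8^(20−k) gives 98.6% (k = 1), 98.2% (k = 2), 97.2% (k = 4) and 96.5% (k = 5).

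**Step 5: illustration for ORR.** Section 1.2.6 gives confirmed vemurafenib response rates of 53% (Phase II) and 48.4% (Phase III). The documents give neither the number exposed, k, nor their response rate, r, so both are assumptions. With b the naive rate:

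expected ORR = [(20 − k) × b + k × r] / 20

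Letting r run from 0 to b:

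| k | b = 53% | b = 48.4% |
|---|---|---|
| 1 | 50.4–53% | 46.0–48.4% |
| 2 | 47.7–53% | 43.6–48.4% |
| 4 | 42.4–53% | 38.7–48.4% |
| 5 | 39.8–53% | 36.3–48.4% |

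With b = 53% and r assumed to be 10–20%:

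- k = 2: (18 × 0.53 + 2 × 0.10)/20 = 0.487, and 0.497 at r = 0.20.
- k = 4: (16 × 0.53 + 4 × 0.10)/20 = 0.444, and 0.464 at r = 0.20.

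One patient is 1/20 = 5 percentage points of the observed rate. Replacing one naive patient by a certain non-responder lowers the expected rate by at most 0.53/20 = 2.65 points. For scale, the binomial standard error at 53% with n = 20 is √(0.53 × 0.47/20) = 0.112, about 11 points.

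**The case against.** The strongest reply is that nothing in the documents shows the situation arising. They describe no adjuvant use of these drugs. The approvals in Sections 1.2.1 and 1.3.1 are for unresectable or metastatic disease, and the prior-vemurafenib sources in Sections 3.3 and 4.1 supply progressors. This stands: the number may be zero.

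A reader might infer more than the text supports:

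- **That the protocol expressly permits adjuvant BRAF or MEK inhibitors, or any adjuvant therapy at all.** Exclusion 6b names no such drug. The permission follows from an unqualified note, exclusions 1 and 4 still apply, and the population sentence can be read as a bar.
- **That Expansion Cohort 2 is defined as inhibitor-free where it is named.** Section 3.2 and Table 8 do not put that condition on PUPs. The conflict is with the synopsis, Section 3.1 and the Figure 5 note.
- **That dose-limiting toxicity findings or the maximum tolerated dose would be distorted.** Table 5 opens every combination escalation cohort to progressors, PTPs and PUPs together, so exposed and naive patients are mixed by design.
- **That pharmacokinetic grouping would go wrong.** Sections 3.5 and 5.5 base the split on progression on vemurafenib immediately before enrolment. A patient who finished adjuvant therapy earlier belongs with the non-progressors.

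It is also fair that the shifts illustrated for a few patients are mostly smaller than the sampling error, that Section 8.2.1 plans no formal efficacy test, and that Section 18 says a study report has been written, so new eligibility wording may come too late. These points limit the weight of the issue. They do not remove the inconsistency between the criteria and the cohort description.

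**Conclusion.** The point holds as a cheap improvement. Read with the PTP definition, Sections 4.2 and 4.3 admit as previously untreated a patient who had an adjuvant BRAF or MEK inhibitor. The synopsis, Section 3.1 and the Figure 5 note describe that expansion group as unexposed. The passages need reconciling because the group's activity is to be set beside historical vemurafenib results.

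The size is unknown. The illustrated response rates rest on assumed counts and assumed response in exposed patients, and must not be read as an estimate of bias in this trial. Tables 13 and 14, the 98.8% figure and the sample size are unaffected.

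**What to change.** 1. In Section 4.3, item 6b, add to the adjuvant note an exception for any BRAF or MEK inhibitor, and put the same condition in Section 4.2, item 6a. This matches the cohort as Section 3.1 and the Figure 5 note state it.
2. Align Section 3.2, the PUP definition under Table 8 and the population sentences in the synopsis and Sections 2.1, 3.1 and 3.1.1.
3. For patients already enrolled, use the prior cancer therapies recorded under Section 5.3.4.1 to flag any PUP with adjuvant BRAF or MEK inhibitor exposure. Show ORR, DOR and PFS for the non-progressor expansion group with and without them. If there are none, one sentence saying so closes the matter.

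The cost is one clause in each of two sections, some alignment of wording and one sensitivity line from data already collected. If enrolment is still open, a few patients would become ineligible. If it has closed, item 3 is the part that still matters.

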4.4 Concomitant Medication and Treatment

4.4.1 Concomitant Therapy

Concomitant therapy includes any prescription medications or over-the-counter preparations used by a patient within 7 days before screening through the study completion visit. Patients who use oral contraceptives, hormone-replacement therapy, or maintenance therapy should continue their use as outlined in the eligibility criteria (see Sections 4.2 and 4.3). Patients who experience toxicities may be treated symptomatically as clinically indicated. All concomitant medications should be recorded on the appropriate electronic Case Report Form (eCRF).

Anti-emetics and anti-diarrheal medications should not be administered prophylactically before initial treatment with study drug. At the discretion of the investigator, prophylactic anti-emetic and anti-diarrheal medication(s) may be used per standard clinical practice before subsequent doses of study drug.

Hematopoietic growth factors (e.g., erythropoietin and granulocyte colony-stimulating factors) and pain medications administered as dictated by standard practice are acceptable while the patient is enrolled in the study. However, growth factors should not be administered prophylactically before initial treatment with study drug; nor should they be used during the DLT observation period.

4.4.2 Excluded Therapy and Food

Use of the following foods and therapies is prohibited during the study (i.e., from 7 days before screening through the study completion visit):

- Grapefruit juice
- St. John's wort or hyperforin
- Any concomitant therapy intended for the treatment of cancer (approved by health authorities or experimental), including chemotherapy, radiation therapy, immunotherapy, hormonal therapy, biologic therapy, investigational agents, or herbal therapy; after Cycle 1, certain forms of radiation therapy may be considered for pain palliation if patients are deriving benefit. Study treatment may be suspended during radiation therapy with agreement by the Medical Monitor.
- Warfarin, anti-thrombotic therapy (except low-molecular weight heparin), or anti-platelet drugs (except low-dose aspirin), prophylactic anticoagulation and/or local application of thrombolytics for patency of venous access devices are allowed as long as INR and aPTT are ≤ 1.5 ULN.
- Quinidine or other anti-arrhythmic agents
- Chronic systemic corticosteroid use (≥ 10 mg of prednisone or equivalent dose of other anti-inflammatory corticosteroids for >7 days) or use of immunosuppressants. However, treatment with systemic corticosteroids during the course of the study for management of toxicity related to vemurafenib and /or cobimetinib (e.g., allergic rash) is allowed.

Patients who require the use of any of these agents will be discontinued from study treatment and followed for safety outcomes for 28 days after the last dose of study treatment or until initiation of another anti-cancer therapy, whichever comes first.

4.4.3 Medication Precautions in Case of Drug–Drug Interactions

Vemurafenib:

On the basis of nonclinical data, vemurafenib may have the potential to cause DDI with concomitant medications that are primarily eliminated by CYP2C9. Patients should be advised to consult with their physician before taking any of the listed medications:

- Non-steroidal anti-inflammatory drugs (e.g., ibuprofen, diclofenac, meloxicam)
- Oral hypoglycemic agents (e.g., tolbutamide, glipizide, glyburide, glimepiride)
- Antihypertensives (e.g., losartan, irbesartan, torsemide)
- Anticonvulsants (e.g., phenytoin)
- Anticoagulants (e.g., warfarin)
- Lipid-lowering drugs (e.g., fluvostatin)

In a CYP450 in vivo metabolism study (NP22676), vemurafenib inhibited CYP1A2 and induced CYP3A4 activity in melanoma patients by approximately 3-fold and 2-fold, respectively. If CYP1A2 substrates must be co-administered with vemurafenib, investigators should assess the safety risk associated with a potential increase in plasma

concentrations of CYP1A2 metabolized drugs. If CYP3A4 substrates must be co-administered with vemurafenib, investigators should monitor the signs of reduced benefit of CYP3A4 metabolized drugs due to a potential decrease in their plasma concentration. Doses of concomitant CYP1A2 and CYP3A4 drugs, but not the dose of vemurafenib, may be adjusted as necessary to alleviate the impact of drug interaction.

For CYP2C9, data suggested that the relatively strong nonclinical signal inhibition, ($IC_{50}=5.9 \mu\text{M}$ in vitro in hepatic microsomes) did not translate to a DDI with this CYP450 isoform. However, vemurafenib was associated with a decrease in clearance of warfarin from plasma, and a 19% increase in the mean exposure (AUC) that did not fall outside of the equivalence boundary.

Little metabolism of vemurafenib (< 10%) was detected in nonclinical studies and in data from a human mass balance study with ^{14}C - vemurafenib in patients with melanoma (Study NP25158). Nonclinical studies suggest that CYP3A4 metabolism and subsequent glucuronidation are responsible for the metabolism of vemurafenib. No clinical data are currently available evaluating the effects of CYP3A4 inducers or inhibitors on vemurafenib exposure.

[Appendix 10](#) includes a non-exhaustive list of typical examples of CYP1A2, CYP3A4, and CYP2C9 substrates and CYP3A4 inducers and inhibitors. A more extensive list of medications can be found online at the following link: <http://medicine.iupui.edu/clinpharm/ddis/Table.asp>. For further information see the Investigator's Brochure.

Cobimetinib:

On the basis of in vitro data showing that cobimetinib is metabolized by the hepatic cytochrome CYP3A4, the drugs listed below should be avoided. If use of one of these drugs is necessary, the risks and benefits and potential alternatives should be discussed with the Medical Monitor prior to its concomitant use with cobimetinib.

- Strong CYP3A4/5 inhibitors such as, but not limited to, atazanavir, clarithromycin, indinavir, itraconazole, ketoconazole, nefazodone, nelfinavir, ritonavir, saquinavir, telithromycin, troleandomycin, and voriconazole
- Strong CYP3A4/5 inducers such as, but not limited to, rifampin, carbamazepine, rifampentine, phenytoin, and Phenobarbital

4.4.4 Medications Affecting QT Interval

Certain medications could affect the results of QT intervals on ECG measurements required in this study. Specifically, anti-emetics other than those belonging to the 5-HT₃ receptor antagonist class (i.e., granisetron, ondansetron, dolasetron, palonosetron) are preferred since the latter has the potential to prolong the QTc interval (see Section 3.10.1). We encourage and recommend that investigators avoid or take precautions in closely monitoring patients who are on medications or herbal and vitamin supplements that may increase QTc interval. Alternative treatment options for medications known to affect QT interval should be discussed with each patient prior to

their inclusion into this study. A complete list of medications that may cause QT interval prolongation is provided in [Appendix 6](#). Please refer to <http://www.azcert.org/> for additional information and references.

